#### *H*1: $P_A \neq P_{P_j}$

Within the model specified above, a comparison will be made of the proportion of  $\geq$ 2-point HDSM-Ax-7 responders at EOT in the sofpironium bromide gel, 15%, and vehicle groups. The estimand of this co-primary efficacy analysis is the difference in proportions between sofpironium bromide gel, 15%, and vehicle with a  $\geq$ 2-point improvement from baseline to EOT in HDSM-Ax-7 total scores among all ITT subjects, regardless of treatment adherence. The comparison will be conducted using a two-sided test at an alpha = 0.05.

A separate, site poolability analysis will be performed with analysis center-by-treatment interaction terms added to the primary analysis model. The overall p-value for the analysis center-by-treatment interaction terms will be determined by averaging the Chi-squared test statistics across the 20 imputations, then calculating the p-value based on that average. An overall p < 0.10 for the combined interaction terms will be regarded as an indication of potential heterogeneity among the analysis centers. A mixed effects logistic regression model analysis will then be performed with analysis center as a random effect to account for the potential heterogeneity. The overall p-value for the analysis center

random effect will be derived from the covariance parameter estimates across the 20 imputations.

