As a secondary, supportive analysis, change from baseline to EOT will be analyzed as a continuous measure. The analysis model will be an ANCOVA model with treatment, baseline HDSM-Ax-7 score, and analysis center as covariates. The estimand for this analysis is the difference in mean baseline to EOT changes in HDSM-Ax-7 total scores between sofpironium bromide gel, 15%, and vehicle arms among all ITT subjects, regardless of treatment adherence.

In addition, a separate site poolability analysis will be performed with analysis center-by-treatment interaction terms added to the primary analysis model. An overall p < 0.10 for the combined interaction terms will be regarded as an indication of potential heterogeneity among the analysis centers. A mixed model analysis will then be performed with analysis center as a random effect to account for the potential heterogeneity.

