#### 8.2.2 Multicenter Studies

Subjects from low enrolling sites will be pooled in order to generate analysis centers. The minimum number of subjects per analysis center is 10. For sites with <10 enrollments, the lowest enrolling site will be combined with the largest enrolling site, and then the second lowest enrolling site and the second largest enrolling site will be combined, and so on. Further combining will be done as necessary until all analysis centers have at least 10 subjects. All analyses that are controlled for site will use this analysis center designation.

Should convergence issues occur due to small cell size for the covariate corresponding to analysis center, the following approach will be followed: a) analysis center will first be re-defined, continuing to group the largest and smallest centers together until there are at least 35 subjects per center; b) If convergence issues still occur after step a) has been completed then analysis center will be re-defined again, continuing to group the largest and smallest centers together until there are at least 70 subjects per center; c) if convergence issues still remain after implementing steps a) and b), the term for analysis center will dropped from the MI algorithm/statistical model.

If the convergence issue occurs in the generation of a MI dataset, all outcomes based on that dataset will use the same analysis center definition. All sensitivity analysis datasets will use the same analysis center definition and the models based off of those datasets will use that analysis center definition.

If the convergence issue occurs in modeling of an outcome, all models for that particular outcome will use the same analysis center definition. For example, if the grouping of at least 70 subjects per analysis center is required for the EOT analysis of  $\geq$ 2-point improvement in HDSM-Ax-7, then all models at all time points of the  $\geq$ 2-point improvement in HDSM-Ax-7 will use that analysis center definition. However, this would not impact the choice of analysis center for  $\geq$ 1-point improvement in HDSM-Ax-7, nor the  $\geq$ 2-point improvement in HDSM-Ax-11.

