#### 8.3 Analysis Methods

With the exclusion of Section 8.3.7 Exploratory Efficacy Analyses, all other Section 8.3 analyses will be repeated for the mITT population.

The primary efficacy analysis will be performed on the ITT population with missing values imputed. The co-primary efficacy outcomes are:

- The proportion of subjects achieving at least a 2-point improvement in the HDSM-Ax-7 scale score from baseline to EOT in the sofpironium bromide gel, 15% group versus vehicle; and
- The change in GSP from baseline to EOT in the sofpironium bromide gel, 15% group versus vehicle.

Both comparisons will be conducted using two-sided tests at an alpha=0.05 level. Both endpoints will need to demonstrate a statistically significant positive result in favor of sofpironium bromide gel, 15% for the study to be considered successful.

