#### *H*1: $\mu_A \neq \mu_P$ ;

The ANCOVA model used in this analysis will be the same, regardless of whether continuous or rank-based GSP data is used. Within the model specified above, a comparison will be made (using LS mean contrasts) to compare the change (or rank-based change) from baseline to EOT for GSP in the sofpironium bromide gel, 15%, and vehicle groups. The estimand of this co-primary efficacy analysis is the mean treatment difference, sofpironium bromide gel, 15%, versus vehicle, in change from baseline (or rank-based change from baseline) to EOT for GSP among all ITT subjects, regardless of treatment adherence. The comparison will be conducted using a two-sided test at an alpha = 0.05.

For the primary endpoint of either ranked or continuous GSP (pending normality test results), a separate, site poolability analysis will be performed with analysis center-by-treatment interaction terms added to the primary analysis model. The overall p-value for the analysis center-by-treatment interaction terms will be determined by averaging the F test statistics across the 20 imputations, then calculating the p-value based on that average. An overall p < 0.10 for the combined interaction terms will be regarded as an indication of potential heterogeneity among the analysis centers. A mixed effect ANCOVA model analysis will then be performed with analysis center as a random effect to account for the potential heterogeneity. The overall p-value for the analysis center random effect will be derived from the covariance parameter estimates across the 20 imputations.

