| 14.2.1.18.1 | Center as a Random Effect - Multiple Imputations  | Intent-to-treat          |
| 14.2.1.18.2 | Site Poolability Analysis 4 for GSP: ANCOVA
Analysis of Change in [Ranked/Continuous] GSP from
Baseline to End of Treatment with Analysis Center as a
Random Effect - Multiple Imputations | Modified Intent-to-treat |
| 14.2.2.1    | Secondary Analysis 1: Subjects Achieving ≥ 1-point
Improvement in HDSM-Ax-7 from Baseline to End of
Treatment - Multiple Imputations  | Intent-to-treat          |
| 14.2.2.2    | Secondary Analysis 1: Subjects Achieving ≥ 1-point
Improvement in HDSM-Ax-7 from Baseline to End of
Treatment - No Imputation   | Per-protocol             |
| 14.2.2.3    | Secondary Analysis 1: Subjects Achieving ≥ 1-point
Improvement in HDSM-Ax-7 from Baseline to End of
Treatment - Multiple Imputations  | Modified Intent-to-treat |
| 14.2.2.4    | Secondary Analysis 2: Subjects Achieving $\geq$ 2-point improvement in HDSM-Ax-7 and 70% Reduction in GSP from Baseline to End of Treatment - Multiple Imputations                                  | Intent-to-treat          |
| 14.2.2.5    | Secondary Analysis 2: Subjects Achieving $\geq$ 2-point improvement in HDSM-Ax-7 and 70% Reduction in GSP from Baseline to End of Treatment - No Imputation   | Per-protocol             |
| 14.2.2.6    | Secondary Analysis 2: Subjects Achieving $\geq$ 2-point improvement in HDSM-Ax-7 and 70% Reduction in GSP from Baseline to End of Treatment - Multiple Imputations                                  | Modified Intent-to-treat |
| 14.2.2.7    | Secondary Analysis 3: Subjects Achieving ≥ 1-point
improvement in HDSM-Ax-7 and 50% Reduction in
GSP from Baseline to End of Treatment - Multiple
Imputations                              | Intent-to-treat          |
| 14.2.2.8    | Secondary Analysis 3: Subjects Achieving $\geq$ 1-point improvement in HDSM-Ax-7 and 50% Reduction in GSP from Baseline to End of Treatment - No Imputation   | Per-protocol             |
| 14.2.2.9    | Secondary Analysis 3: Subjects Achieving $\geq$ 1-point
improvement in HDSM-Ax-7 and 50% Reduction in
GSP from Baseline to End of Treatment - Multiple
Imputations                         | Modified Intent-to-treat |

| Number    | Title   | Population      |
|-----------|---|-----------------|
| 14.2.3.1  | Subjects Achieving $\geq$ 1-point Improvement in HDSM-
Ax-7 by Visit   | Intent-to-treat |

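### The follow-up to a flagged centre-by-treatment interaction names only centre as random, so as written it does not account for a treatment effect that varies by centre

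*SAP*

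**What the plan says.** Both primary models contain analysis centre: as a covariate in the HDSM-Ax-7 logistic regression (SAP 8.3.1) and as a fixed effect in the GSP ANCOVA (SAP 8.3.2).

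The poolability check is a different model: "A separate, site poolability analysis will be performed with analysis center-by-treatment interaction terms added to the primary analysis model". An overall interaction p < 0.10 counts as a sign of heterogeneity between centres. The response, for both endpoints, is a mixed model "with analysis center as a random effect to account for the potential heterogeneity". Protocol 10.3.1 reads "A mixed model analysis will then be performed with analysis center as a random effect to account for the potential heterogeneity", and protocol 10.3.2 says the same for GSP.

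The only p-value specified for the follow-up concerns centre. SAP 8.3.2 states: "The overall p-value for the analysis center random effect will be derived from the covariance parameter estimates across the 20 imputations". SAP 8.3.1 has the same sentence.

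Nothing in the protocol or SAP text keeps the interaction in the mixed model, adds a random centre-by-treatment term, or plans centre-specific treatment effects.

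**The concern.** What triggers the follow-up is evidence that the treatment effect differs between centres. A random centre effect describes something else, namely centres whose outcomes sit higher or lower in both arms. The primary models already remove those differences. The SAP therefore answers a flagged interaction with a model that has no term for it, and attaches a p-value for a different quantity.

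What is at stake is interpretation. A study report that follows the SAP would show a nearly unchanged treatment effect and describe it as having accounted for the heterogeneity.

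**Working it through.** **Inputs from the documents.** About 350 randomised, with site-stratified 1:1 allocation (protocol 11.1.3). GSP difference 73 mg with SD 170, or 16.6 ranks with SD 39.5; HDSM-Ax-7 response 29.8% v 53.7% (SAP 2.6). "Both comparisons will be conducted using two-sided tests at an alpha=0.05 level" (SAP 8.3). At least 10 subjects per centre, so at most 350/10 = 35 centres. If models do not converge, SAP 8.2.2 goes on "continuing to group the largest and smallest centers together until there are at least 35 subjects per center", and then to 70: 350/35 = 10 centres, 350/70 = 5. **Assumed:** all between-centre SDs, because the documents give none.

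**1. The plan's own figures.** GSP: 2 × (1.960 + 1.645)² × 39.5²/16.6² = 147.2, so 148 per arm, as stated. HDSM-Ax-7: 108 per arm without and 116 with continuity correction; the SAP gives 116. The inputs are read correctly. The standardised GSP effect is 73/170 = 0.43 (ranks: 16.6/39.5 = 0.42). The planned log odds ratio is ln(0.537/0.463) − ln(0.298/0.702) = 1.005.

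**2. Algebra for GSP.** With balance within centre, treatment is nearly orthogonal to centre. Let σ be the residual SD, τ the between-centre SD of the treatment effect and C the number of centres.
- Centre fixed, or centre random only: SE² ≈ 4σ²/N. With σ = 170 and N = 350, SE = 18.2 mg.
- An omitted interaction only leaks τ²/4 into the residual. At τ = 73 mg, SE = √(4 × (170² + 73²/4)/350) = 18.6 mg in both models.
- With a random centre-by-treatment term: SE² = 4σ²/N + τ²/C. At τ = 73 mg and C = 10, SE = √(330.3 + 532.9) = 29.4 mg.

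**3. GSP simulation, all trials (mg scale, 200 per setting).** With 10 centres and τ = 0, 36.5 or 73 mg, the fixed-centre and random-centre estimates differed by 0.06 to 0.07 mg on average. Their mean SEs were identical (18.1, 18.2, 18.6). Adding the random centre-by-treatment term gave 19.5, 21.5 and 28.5. With 25 centres only τ = 0 was completed: difference 0.12 mg, SE 18.2 for both.

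**4. GSP simulation, flagged trials only** (1,500 per scenario, 138 to 772 flagged; 10 or 25 centres; τ up to 0.3 residual SD, which is 0.3/0.43 = 70% of the planned effect). SE ratio, random-centre to fixed-centre: 0.998 to 1.000. Same 5% verdict: 99.5 to 100%. Pooling 20 vehicle-based imputations by Rubin's rules (200 trials, not restricted to flagged ones; imputation model assumed, because the flow charts in SAP 18.2 and 18.3 are not in the text) gave a median SE ratio of 1.000.

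**5. HDSM-Ax-7.** Flagged trials with 5 or 10 centres (600 per scenario): log odds ratio 1 to 3% smaller in the mixed model, SE 1 to 2% smaller, same verdict in 99.4 to 100%. A separate run of about 150 trials per setting, flagged or not, gave:

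| Centres | SD of log OR between centres | Mean log OR, fixed / random centre | Ratio | Median SE, random centre | Empirical SD, random centre |
|---|---|---|---|---|---|
| 10 | 0 | 1.020 / 0.990 | 0.97 | 0.230 | 0.236 |
| 10 | 0.5 | 1.052 / 1.021 | 0.97 | 0.234 | 0.301 |
| 10 | 1.0 | 1.038 / 1.007 | 0.97 | 0.236 | 0.392 |
| 25 | 0 | 1.104 / 1.022 | 0.93 | 0.232 | 0.234 |
| 25 | 0.5 | 1.082 / 1.002 | 0.93 | 0.232 | 0.236 |
| 25 | 1.0 | 1.088 / 1.008 | 0.93 | 0.236 | 0.283 |

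With 25 centres the fixed-centre value is about 8% larger, so the random-centre value is about 7% smaller. The ratio depends on the number of centres and not on heterogeneity.

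**6. What the centre p-value detects.** Proportion of flagged GSP trials with centre p < 0.05, 10/25 centres. SDs are in units of residual SD; level means the centre mean averaged over arms.

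| Level SD | Effect SD | Wald | Likelihood ratio |
|---|---|---|---|
| 0.3 | 0 (false flag) | 41% / 70% | 91% / 86% |
| 0.3 | 0.3 | 36% / 67% | 86% / 83% |
| 0 | 0.3 | 0% / 1% | 2% / 5% |
| Effects vary in the active arm only | 0.3 | 1% / 9% | 36% / 22% |

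The p-value follows level differences. It responds to effect variation only in part, when that variation also shifts the centre mean.

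**The case against.** **The text is silent rather than wrong.** SAP 8.3.1 and 8.3.2 do not list the mixed model's terms, and by convention a statistician may treat the interaction as random once centre is. That is fair, and it limits the point to the wording. However, SAP version 2.0 returned to these sections to specify p-values and specified one for centre only. A programmer following the text would fit a random intercept.

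**Table titles.** A reader might take the planned title of Table 14.2.1.18.1, ending "Center as a Random Effect - Multiple Imputations", as proof that no interaction is fitted. It proves little: the titles of Tables 14.2.1.15 and 14.2.1.17 do not mention interaction either, although the text requires it there. Table specifications are in a separate document.

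**The standard error.** A reader might infer that the follow-up interval is too narrow. For the SAP's estimand, all ITT subjects, it is not: in flagged GSP trials with level and effect SDs of 0.3, its 95% interval covered 96% (10 centres) and 94% (25). Coverage of 88% and 92% arises only if the target is an average over centres, which the SAP does not state.

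**Size of the p-value problem.** The likelihood-ratio rates look most striking, but a p-value "random effect will be derived from the covariance parameter estimates across the 20 imputations" reads as Wald-type, so 41% / 70% is the fairer figure for false flags. The pattern is the same under either test.

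**It is supportive, and the flag stays visible.** Both are true. The interaction results have their own tables, 14.2.1.15 and 14.2.1.17. What is lacking is a follow-up that does what its description says.

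**Conclusion.** The point holds as a defect in a supportive analysis and should be corrected. For GSP, the prespecified response to a flagged interaction reproduces the primary treatment estimate and SE almost exactly. For HDSM-Ax-7 the two models are similar but not identical, and the gap comes from the number of centres. The specified p-value mainly reflects differences in level.

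It would go too far to say that the trial's conclusion is at risk. The step does not enter the co-primary tests, the success rule or the fixed-sequence testing of secondary endpoints.

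The structural conclusion rests on the wording and on near-balance within centre. The coverage, p-value and interval-width figures depend on the assumed SDs. The 1 to 3% figure for HDSM-Ax-7 applies to 5 or 10 centres, that is, to the fallback groupings and not the default minimum of 10 subjects per centre.

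**What to change.** In SAP 8.3.1 and 8.3.2, specify that the follow-up model has random effects for analysis centre and for centre-by-treatment. Report:
- the treatment effect with its confidence interval, pooled by Rubin's rules;
- the between-centre variance of the treatment effect, in place of the centre-effect p-value;
- descriptive centre-specific treatment effects.

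Label this as a supportive analysis for an average over centres, so that it is not read as a correction to the ITT estimand. Its coverage was examined only for the average-over-centres target (GSP: 96 to 100% after a flag). Record the change in SAP Section 13. A protocol amendment is not needed, because SAP Section 1 allows departures from the protocol to be documented in the SAP before database lock.

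The cost is wording, minor programming and a wider supportive interval. In flagged trials, under the assumed SDs, it was 1.27 to 1.34 times (25 centres) or 1.59 to 1.75 times (10 centres) the centre-only interval for GSP. For HDSM-Ax-7 it was 1.6 to 1.8 times (10 centres) or 2.1 to 2.5 times (5 centres). With about 5 centres the variance estimate will be imprecise. The logistic model may have convergence problems; none occurred in 6,000 simulated fits with 5 or 10 centres, but other software may differ.

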### 8.3.2 Primary Analysis of the GSP Co-Primary Endpoint

The primary analysis of the GSP co-primary endpoint will use all available GSP change from baseline scores at EOT. Missing baseline continuous GSP data (i.e. missing data for all Visits of 2, 3, 4) will be imputed using the Screening GSP data. If Screening GSP data is also missing, subject will be excluded from all GSP change from baseline analyses.

For GSP change from baseline to EOT data, univariate checks will be performed prior to performing multiple imputations for missing data. The Shapiro-Wilk test will be applied to assess Normality of the model residuals separately for sofpironium bromide gel, 15% arm, and vehicle arm. Should the assumption of Normality not be violated for both treatment arms, then GSP change from baseline to EOT values will be analyzed as continuous data. The median of continuous GSP data from Visits 2, 3, and 4 will be used as the baseline value for a subject, and the median of continuous GSP data from Visits 10, 11, and 12 will be used as the EOT value. For each subject, the difference between the baseline and EOT GSP values (EOT – baseline) will serve as the outcome value for the GSP ANCOVA analysis.

Should the assumption of Normality be violated for either treatment arm, the GSP change from baseline to EOT values will be rank-transformed for both arms. For the rank-transformation of GSP measurements at a particular timepoint, continuous data for all subjects will be ranked together without regard to treatment assignment, from smallest to highest value. The smallest observation will be assigned the rank of 1, the second smallest the rank of 2, and so on. Average ranks will be used for tied observations. For determination of baseline value for a subject, the continuous GSP data will be ranked separately at each of Visits 2, 3, and 4; the median of the three ranks will be used as baseline value of the subject. Using the measurement data from Visits 10, 11, and 12, the rank-transformed GSP value at EOT will be derived in the same manner. For each subject, the difference between the rank-transformed baseline and EOT GSP values (EOT – baseline) will serve as the outcome value for the rank-based GSP ANCOVA analysis.

Missing EOT GSP data (continuous data), for each of Days 41, 42, and 43 will be imputed before analysis is performed for subjects missing both axillae at all 3 visits. If at least one axillae is non-missing at Day 41, 42, or 43, then the EOT value will be considered non-missing. For continuous data, subjects with results (Section 8.2.1.2) meeting the criterion for "outlier" will be removed from imputation sampling database (i.e., data for vehicle subjects) prior to missing data imputation. From the appropriate imputation sampling database, multiple imputations of missing EOT sofpironium bromide gel, 15% arm GSP values will be performed using a CBI methodology (Section 8.2.1.1 and Appendix 18.3). Multiple imputations assuming MAR will be performed for missing EOT data Vehicle subjects.

The model specified is an ANCOVA model (either non-ranked or ranked).

The following fixed effects are planned:

- Treatment (class effect: sofpironium bromide gel, 15% group, vehicle)
- Baseline GSP (either non-ranked or ranked)
- Analysis center (see Section 8.2.2)

The null hypothesis to be tested for the primary analysis of the GSP Co-primary endpoint is as below:

H0: The GSP changes (or rank-based changes) from baseline to EOT are the same in the sofpironium bromide gel, 15%, and vehicle groups, i.e.

*H*0: 
$$\mu_A = \mu_P$$
;

where  $\mu_A$  and  $\mu_P$  represent the true mean change (or rank-based change) in GSP scores for Treatment A (sofpironium bromide gel, 15%) and Treatment P (vehicle), respectively.

The null hypothesis will be tested against the two-sided alternative hypothesis as below:

H1: The GSP changes (or rank-based changes) from baseline to EOT are not the same in the sofpironium bromide gel, 15%, and vehicle groups, i.e.

#### *H*1: $\mu_A \neq \mu_P$ ;

The ANCOVA model used in this analysis will be the same, regardless of whether continuous or rank-based GSP data is used. Within the model specified above, a comparison will be made (using LS mean contrasts) to compare the change (or rank-based change) from baseline to EOT for GSP in the sofpironium bromide gel, 15%, and vehicle groups. The estimand of this co-primary efficacy analysis is the mean treatment difference, sofpironium bromide gel, 15%, versus vehicle, in change from baseline (or rank-based change from baseline) to EOT for GSP among all ITT subjects, regardless of treatment adherence. The comparison will be conducted using a two-sided test at an alpha = 0.05.

For the primary endpoint of either ranked or continuous GSP (pending normality test results), a separate, site poolability analysis will be performed with analysis center-by-treatment interaction terms added to the primary analysis model. The overall p-value for the analysis center-by-treatment interaction terms will be determined by averaging the F test statistics across the 20 imputations, then calculating the p-value based on that average. An overall p < 0.10 for the combined interaction terms will be regarded as an indication of potential heterogeneity among the analysis centers. A mixed effect ANCOVA model analysis will then be performed with analysis center as a random effect to account for the potential heterogeneity. The overall p-value for the analysis center random effect will be derived from the covariance parameter estimates across the 20 imputations.

